4.1.5. Adapted ATP cohort

When presenting different time points, the Adapted ATP cohort will be used to denote that for each time point, the corresponding ATP cohort for immunogenicity has been used.

More specifically,

- The analyses on the pre and post booster dose time points in mothers, and the cord blood sample will be based on the ATP cohort for immunogenicity in study 116945 (Boostrix-047)
- The analysis on the pre and post primary time points in infants will be based on the ATP cohort for immunogenicity in study 201330 (Boostrix-048).
- The analysis on the pre and post booster time points in infants will be based on the ATP cohort for immunogenicity in study 201334 (Boostrix-049).

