### 10.3. Determination of sample size

The sample size for this study is not derived from any power based calculation. The number of evaluable subjects for the study is based on the all infants who are willing to take part in the current study. Considering approximately 20-40% reduction in the number of evaluable subjects due to dropouts and protocol violations from the primary study, [Table 16](#) gives the estimated sample size of evaluable subjects that can be expected and the precision achieved with this sample for various expected values of seroprotection/booster response rates in terms of exact 95% confidence interval (CI).

**Table 16 Exact 95% CI of the different values of observed response rate (booster response rate or seroprotection rate) for a sample size of 204-272 subjects)**

Number of evaluable subjects	Observed seroprotection/response rate expressed as a percentage	Exact 2-sided 95% CI for this observed rate for a sample size of 204-272 subjects	
		Lower Limit (LL)	Upper Limit (UL)
272	80	74.9	84.7
	86	81.3	89.9
	92	88.4	95.2
	93	89.3	95.7
	94	90.6	96.6
	95	92.0	97.4
	96	92.9	98.0
	97	94.3	98.7
	98	95.8	99.4
	99	97.4	99.9
238	100	98.7	100.0
	80	74.6	85.1
	86	81.1	90.3
	92	87.8	95.1
	93	89.3	96.1
	94	90.3	96.7
	95	91.4	97.4
	96	92.9	98.3
	97	94.0	98.8
	98	95.8	99.5
204	99	97.0	99.9
	100	98.5	100.0
	80	74.3	85.6
	86	80.8	90.7
	92	87.6	95.5
	93	88.8	96.2
	94	90.0	96.9
	95	91.2	97.6
	96	92.4	98.3
	97	93.7	98.9
98	95.1	99.5	
99	96.5	99.9	
100	98.2	100	

Reference study:

DTPa-HBV-IPV 095 (Germany): Group primed with *Infanrix hexa* according to 2, 4, 6 schedule and received a booster dose of *Infanrix hexa* between 11-23 months.

DTPa-HBV-IPV 083 (Spain): Group primed with *Infanrix hexa* according to 2, 4, 6 schedule and received a booster dose of *Infanrix hexa* between 18-20 months of age.

DTPa-HBV-IPV 081 (Germany): Group primed with *Infanrix hexa* according to 3, 4, 5 schedule and received a booster dose of *Infanrix hexa* between 12-23 months of age.

The reference values (booster phase) considered for the above calculations are presented in [Table 17](#).

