The immunogenicity analysis for the pertussis antigens will be generated on the adapted ATP cohort taking in to account all the time points from the study Boostrix 047 up to the current study.

The kinetics of the observed GMCs of the pertussis antigens across all the time points will be plotted in an evolution graph with confidence interval.

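### The pertussis evolution graph changes cohort at two junctions between studies, so apparent antibody decay or waning there can partly reflect a change of membership

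*SAP*

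**What the plan says.** SAP 4.1.5 defines the Adapted ATP cohort by the rule that "for each time point, the corresponding ATP cohort for immunogenicity has been used". It then assigns the cohorts study by study:

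- **Study 047 (116945):** the "pre and post booster dose time points in mothers, and the cord blood sample will be based on the ATP cohort for immunogenicity" of that study.
- **Study 048 (201330):** "The analysis on the pre and post primary time points in infants will be based on the ATP cohort for immunogenicity in study 201330".
- **Study 049 (201334):** "The analysis on the pre and post booster time points in infants will be based on the ATP cohort for immunogenicity in study 201334".

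SAP 5.3.2 applies this cohort to the pertussis antigens, "taking in to account all the time points from the study Boostrix 047 up to the current study", and specifies the display: "The kinetics of the observed GMCs of the pertussis antigens across all the time points will be plotted in an evolution graph with confidence interval".

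SAP 4.2.2.1 and 4.2.3.1 carry eliminations from 048 into 049, except three visit-specific codes: 2090 (blood-sampling interval), 2100 (no post-vaccination serology) and 2120 (incoherent or erroneous data). Neither document plans a version of the graph restricted to infants common to the cohorts, or a note that membership changes along the curve.

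**The concern.** A line joining GMCs over time, described as kinetics, will be read as the course of antibody in one set of children. Where the line passes from one study to the next it is not that. Infants drop out between studies. In addition, an infant outside the 048 ATP cohort solely under code 2090, 2100 or 2120 can enter the 049 ATP cohort. A step across such a junction therefore contains two things, change in antibody and change in who is counted, and the interval drawn at each point does not cover the second.

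Two readings are exposed. One is the post-primary to pre-booster decline, which readers will take as waning. The other is the comparison of post-primary with post-booster levels. The Protocol background (1.1) raises that comparison when it cites lower primary responses in infants of vaccinated mothers that were no longer seen after the booster. If losses differed by group or by priming schedule, the distortion could differ too, but the documents give no information on that.

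**Working it through.** **Step 1. Which steps change cohort.** SAP 4.1.5 gives seven time points, hence six adjacent steps.

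| Step | Cohorts | Change? |
|---|---|---|
| Maternal pre to maternal post | 047 to 047 | No |
| Maternal post to cord | 047 to 047 | No |
| Cord to infant pre-primary | 047 to 048 | **Yes** |
| Pre-primary to post-primary | 048 to 048 | No |
| Post-primary to pre-booster | 048 to 049 | **Yes** |
| Pre-booster to post-booster | 049 to 049 | No |

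**Step 2. How far the cohorts overlap.** Inherited eliminations and the requirement for a complete 048 primary series make the 049 ATP cohort largely a subset of the 048 ATP cohort. The three exempt codes mean it is not strictly one. From mother to infant, the only elimination the SAP describes as inherited from the mother is code 1060. The actual overlap is not reported for either junction.

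**Step 3. The plan's own loss figure.** Protocol 10.3 introduces its precision table with "Considering approximately 20-40% reduction in the number of evaluable subjects due to dropouts and protocol violations from the primary study". Applied to the maximum of 340 per group, this gives 340 × 0.80 = 272, 340 × 0.70 = 238 and 340 × 0.60 = 204, which are the three sample sizes in Table 16. It is a planning allowance on 049 enrolment, not a measured 048-to-049 loss. It serves below only as a proxy for the second junction. No corresponding figure exists for the first.

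**Step 4. Effect on a step.** Let s be the share of the earlier cohort that is lost, and R the ratio of the stayers' GMC to the leavers' GMC at the earlier time point. A GMC is the antilog of a mean log, so:

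- GMC(all, earlier) = GMC(stayers, earlier) × R^(−s)
- plotted later/earlier ratio = within-infant ratio × R^s

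This covers leavers only. Infants entering through the three exempt codes would add a further term. R is an assumption, because the documents give no value.

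| R | s = 0.20 | s = 0.40 |
|---|---|---|
| 0.5 | 0.871 | 0.758 |
| 0.8 | 0.956 | 0.915 |
| 1 | 1.000 | 1.000 |
| 1.25 | 1.046 | 1.093 |
| 1.5 | 1.084 | 1.176 |
| 2 | 1.149 | 1.320 |

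As an example, suppose a true ten-fold decline. With R = 2 it would be drawn as 10/1.149 = 8.7-fold to 10/1.320 = 7.6-fold. With R = 0.5 it would be drawn as 10/0.871 = 11.5-fold to 10/0.758 = 13.2-fold.

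**Step 5. Scale.** The 95% CI factor of one GMC is 10^(1.96 × SD/√n). At an assumed log10 SD of 0.4 it is 1.116 for n = 272 and 1.135 for n = 204. Over SDs of 0.3 to 0.6 it runs from 1.086 to 1.209. A factor of 1.05 to 1.09 is therefore mostly smaller than the plotted uncertainty, and only at the narrowest intervals about the same size. A factor near 1.3 is larger.

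**The case against.** The strongest reply is that little depends on the affected steps. All analyses are descriptive. Persistence is a secondary objective answered by pre-booster levels in the 049 ATP cohort alone, and no endpoint is defined as a change from post-primary to pre-booster. Between-group comparison at any single time point uses one cohort rule for both groups. The carried-over eliminations keep the infant cohorts close. The SAP is also open about the choice: it names and defines the Adapted ATP cohort. All of this stands, and it limits the point to the reading of one added graph and its table.

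The reply is also right about size. The 20-40% is a planning allowance and R has no source in the documents, so no distortion can be claimed as expected.

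A reader might infer from the SAP 4.1.5 rule that the cohort differs at every time point, so that the booster rise itself is confounded. The documents do not support that. Pre- and post-primary share the 048 ATP cohort, and pre- and post-booster share the 049 ATP cohort. Pertussis booster response, the primary pertussis endpoint, is counted in infants with both results (Template 13). What remains within a study is missing samples: 049 ATP entry needs only one post-vaccination antigen result, and missing serology is not replaced. That is a separate and smaller matter.

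The reply does not remove the need to separate membership from antibody at the two junctions when the graph is offered as kinetics.

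**Conclusion.** The point holds for two of the six steps: cord to pre-primary, and post-primary to pre-booster, together with any comparison that spans the latter. There the graph is not within-subject, and no planned display shows whether that matters.

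Its size is unknown. It is nil if leavers and stayers have equal GMCs. Under the illustrative assumptions, with Protocol 10.3's 20-40% standing in for the real loss and a 1.25- to 2-fold GMC difference, the factor is about 1.05 to 1.32 if leavers are lower, with the reciprocal range if they are higher. Neither the direction nor a difference between groups can be inferred from the documents.

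The primary endpoints and the within-study pre-to-post steps are not affected by cohort change. This is an inexpensive improvement to a descriptive display, not a flaw in the main analysis.

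**What to change.** Keep the Adapted ATP graph and show N at each time point. The pertussis GMC table mock (Template 10) already has an N column; the mock of the graph itself (Template 32) is not visible in the text available here, so whether it shows N cannot be judged.

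Add one descriptive figure and table of pertussis GMCs by group, limited to infants in both the 048 and 049 ATP cohorts with pertussis results at all four infant time points, plus their linked maternal and cord samples where available. Label it as a sensitivity display, and state in a footnote to the main graph where the cohort changes.

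The cost is one figure and one table from data already held. The downsides are a smaller N and a complete-case subset conditioned on remaining to the 049 ATP cohort, whose early GMCs need not match those reported for 047 and 048. That is why it should sit beside the planned graph rather than replace it. A repeated-measures model would be an alternative, but in an all-descriptive plan it is a trade-off and not required.

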4.2. Criteria for eliminating data from Analysis Sets

Elimination codes are used to identify subjects to be eliminated from analysis. Detail is provided below for each set.

4.2.1. Elimination from Total Vaccinated cohort (TVC)

Code 1030 (Study vaccine not administered at all) and code 900 (invalid informed consent or fraudulent data) will be used for identifying subjects eliminated from TVC.

4.2.2. Elimination from ATP cohort for safety

4.2.2.1. Excluded subjects

All eliminations from the study 201330 [DTPA (BOOSTRIX)-048 PRI] will be applicable for this follow up study except for the visit specific elimination codes (2090, 2100 and 2120).

A subject will be excluded from the ATP cohort for safety and immunogenicity under the following conditions

Code	Condition under which the code is used	Visit (timepoints) where the code is applicable	Applicable for analysis set (Safety, immunogenicity)
800	Fraudulent data. Also inherited from the 048 study	all	all
900	Invalid informed consent or fraudulent data Also inherited from the 048 study.	all	all
1030	Study vaccine not administered at all. Also inherited from the 048 study.	Visit 2	Safety, immunology
1040	Administration of concomitant vaccine(s) forbidden in the protocol 
 • Concurrently participating in another clinical study, within three months prior to the booster vaccine dose and at any time during the present booster study, in which the subject has been or will be exposed to an investigational or a non-investigational vaccine/product (pharmaceutical product or device). • A vaccine not foreseen by the study protocol administered during the period starting from 30 days before the booster dose of study vaccine and ending 30 days after*, with the exception of inactivated influenza vaccine and other vaccines given as a part of the national/regional immunisation schedule, that are allowed at any time during the study period. 
*In case an emergency mass vaccination for an unforeseen public health threat (e.g.: a pandemic) is organised by the public health authorities, outside the routine immunisation program, the time period described above can be reduced if necessary for that vaccine provided it is licensed and used according to its SPC or Product Information (PI) and according to the local governmental recommendations and provided a written approval of the Sponsor is obtained.
	Visit 2	Safety, immunology

CONFIDENTIAL

	Also inherited from the 048 study.		
1050	Randomisation failure (subject who received a vaccine not compatible with randomization) Also inherited from the 048 study.	Carried forward from previous study	Safety, immunology
1060	Randomisation code broken at the investigator site OR at GSK Safety department. This code is inherited from the mother. Also inherited from the 048 study.	Visit 2	Safety, immunology
1070	Vaccination not according to protocol Site or route of study vaccine administration wrong or unknown. Also inherited from the 048 study.	Visit 2	Safety, immunology
1080	Vaccine temperature deviation (vaccine administration not as per protocol) => Infanrix hexa vaccine administered despite a Good Manufacturing Practices (GMP) no-go temperature deviation. Also inherited from the 048 study.	Visit 2	Safety, immunology
1090	Expired vaccine administered (vaccine administration not as per protocol)=> Subjects who received an expired Infanrix hexa . Also inherited from the 048 study.	Visit 2	Safety, immunology

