3.2. Secondary objectives

- To assess the persistence of antibodies to all vaccine antigens before the booster dose in infants born to mothers vaccinated with *Boostrix* during pregnancy or immediately post-delivery.
- To assess the immunological response to *Infanrix hexa* and *Prevenar 13* in terms of antibody concentrations or titres against all antigens, one month after the booster dose in infants born to mothers vaccinated with *Boostrix* during pregnancy or immediately post-delivery.
- To assess the immunological response to *Infanrix hexa* in terms of seropositivity rates against pertussis antigens, one month after the booster dose in infants born to mothers vaccinated with *Boostrix* during pregnancy or immediately post-delivery.
- To assess the safety and reactogenicity of *Infanrix hexa* and *Prevenar 13* in terms of solicited and unsolicited symptoms and serious adverse events (SAEs).
- To assess the neurodevelopmental status of infants born to mothers vaccinated with *Boostrix* during pregnancy or immediately post-delivery, at 9 and 18 months of age.

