4.1.3. According-to-protocol cohort for analysis of safety

The ATP cohort for analysis of safety will include all subjects from the TVC who complied with the vaccine administration:

- who have received all vaccine doses in the primary study 201330 [DTPA (BOOSTRIX)-048 PRI].
- who have received the booster dose of study vaccines in the current study.
- for whom administration route and site of study vaccines is known and according to the protocol.
- who have not received a vaccine not specified or forbidden in the protocol.

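### Exclusion codes 1080 and 1090 cover only Infanrix hexa, so infants given expired or temperature-deviated Prevenar 13 stay in the ATP pneumococcal results; for an omitted Prevenar 13 dose, definition and codes do not match

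*SAP*

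**What the plan says.** SAP 4.2 makes elimination codes the means of identifying the subjects to be removed. Four codes in SAP 4.2.2.1 deal with the vaccine dose:

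- **1030:** "Study vaccine not administered at all". SAP 4.2.1 uses the same code to remove subjects from the TVC.
- **1070:** "Site or route of study vaccine administration wrong or unknown". No product is named.
- **1080:** "Infanrix hexa vaccine administered despite a Good Manufacturing Practices (GMP) no-go temperature deviation".
- **1090:** "Expired vaccine administered (vaccine administration not as per protocol)=> Subjects who received an expired Infanrix hexa".

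The ATP safety definition in SAP 4.1.3 (and protocol 10.4.3) covers subjects "who have received the booster dose of study vaccines in the current study". Protocol Table 9 lists both Infanrix hexa and Prevenar 13 as study vaccines. SAP 4.2.3.1 carries every exclusion from the ATP safety cohort into the ATP immunogenicity cohort.

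SAP 3.2 includes this objective, which refers to the post-booster sample: "To assess the immunological response to *Infanrix hexa* and *Prevenar 13* in terms of antibody concentrations or titres against all antigens, one month after". SAP 5.3.1 and 5.3.2 report the pneumococcal rates, GMCs and percentages at or above 0.35 µg/mL on the single ATP immunogenicity cohort. No separate pneumococcal set is defined.

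**The concern.** A storage or expiry fault is handled differently depending on which syringe it affects. With Infanrix hexa, the infant leaves both ATP cohorts and so drops out for every antigen. With Prevenar 13, the infant stays, and the post-booster pneumococcal values count as according to protocol. If the faulty dose boosts poorly, pneumococcal GMCs and threshold percentages are pulled down.

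For an omitted Prevenar 13 dose the risk is inconsistency. A programmer following the codes would keep the infant, leaving an unboosted child in the pneumococcal rows. A programmer following the text of 4.1.3 would remove the infant everywhere, including from the primary Infanrix hexa analyses, where those data are informative. The SAP does not say which is intended.

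**Working it through.** **1. Faults set against the rules (Prevenar 13 booster only; Infanrix hexa given correctly)**

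| Prevenar 13 fault | SAP 4.1.3 definition | Code that fires | Result |
|---|---|---|---|
| Wrong or unknown site or route | Excluded | 1070 | Out of both ATP cohorts |
| Expired | No specific criterion | None (1090 names Infanrix hexa) | Stays in |
| Temperature-deviated | No specific criterion | None (1080 names Infanrix hexa) | Stays in |
| Not given | Excluded (booster dose of both products required) | None clearly (1030 needs no vaccine at all) | Definition and codes disagree |

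**2. Do other rules close the gap?**

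- SAP 4.1.4 asks for a post-vaccination result for at least one antigen, so Infanrix hexa serology alone qualifies an infant.
- Code 2080 (vaccination schedule) is only carried forward from the primary study.
- Code 2090 checks the blood sample date against Visit 2, not the condition of any dose.
- Code 2120 (incoherent or abnormal serology) depends on the result and is not a dosing rule.
- The complementary TVC immunogenicity analysis keeps the same infants, so it gives no clean comparison.

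**3. Can code 1030 be read as applying to either vaccine?** No. It also defines removal from the TVC (SAP 4.2.1). Read that way, it would drop an infant who received Infanrix hexa from the TVC, which is the primary safety set (SAP 5.4.1) and is meant to hold all vaccinated subjects (SAP 4.1.2).

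**4. Possible size**

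The plan gives no figure for this effect, so there is none to reproduce. The evaluable numbers per group follow from protocol 10.3: 340 × (1 − 0.40) = 204 and 340 × (1 − 0.20) = 272.

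Assumptions that are not in the documents: k infants per group have a faulty or missing Prevenar 13 dose, they show no boosting at all, and the booster otherwise raises concentrations R-fold, with R from 3 to 10. With f = k/N, the mean log concentration falls by f × log R, so the GMC is multiplied by R^(−f). A threshold rate moves by at most f.

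| k | N | f | GMC multiplier, R = 3 | R = 5 | R = 10 |
|---|---|---|---|---|---|
| 1 | 272 | 0.37% | 0.996 | 0.994 | 0.992 |
| 1 | 204 | 0.49% | 0.995 | 0.992 | 0.989 |
| 5 | 272 | 1.84% | 0.980 | 0.971 | 0.959 |
| 5 | 204 | 2.45% | 0.973 | 0.961 | 0.945 |

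One infant lowers a GMC by 0.4% (1 − 0.996) to 1.1% (1 − 0.989), and a rate by at most 0.4-0.5 points. Five lower a GMC by 2.0% (1 − 0.980) to 5.5% (1 − 0.945), and a rate by at most 1.8-2.5 points.

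**The case against.** A reader might infer that every infant without a valid Prevenar 13 booster remains in the ATP results. The documents do not support that. The wording of 4.1.3 already shuts out an omitted dose, SAP 4.2.3.1 refers back to that section, and code 1070 catches a wrong or unknown site or route for either product. This objection stands and limits the point to expired or temperature-deviated doses, plus a mismatch for omitted ones.

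Four further arguments deserve a hearing.

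- *The codes may be meant generically.* The mock table in Template 5 labels 1080 and 1090 without naming a product, and the heading of 1070 speaks broadly of vaccination not according to protocol. But the templates are illustrative, while the operative table in 4.2.2.1 restricts each code explicitly. This does not remove the gap.
- *A general phrase in 4.1.3 could be used.* Its opening line asks for compliance with vaccine administration. That might be stretched to a spoiled dose, but none of the listed criteria says so, and the same fault with Infanrix hexa was thought to need its own code.
- *Cases should be rare.* Protocol 6.2 bars use of product affected by an excursion outside 0.0 to +8.0°C until the sponsor approves. This stands. The calculation is also close to a worst case, since nothing in the documents says that such a dose produces no response.
- *Little depends on it.* The primary endpoints concern Infanrix hexa antigens only, and every analysis is descriptive. This stands and sets the weight of the point.

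**Conclusion.** The point holds in a limited form. As written, the rules keep an infant given expired or temperature-deviated Prevenar 13 in the ATP pneumococcal results. For an omitted Prevenar 13 dose, the definition excludes the infant but no code clearly does so. That is an ambiguity, not demonstrated contamination.

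The true size cannot be known from the documents, which give neither the number of such infants nor the fold-rise. The GMC reductions above (about 0.4-1.1% for one infant, about 2.0-5.5% for five) rest on assumed values and on zero response to the faulty dose. A fault confined to one site could weigh more in the by-schedule tables, but the documents give no subgroup sizes from which to calculate that. With secondary, descriptive endpoints and a small, contingent effect, this is a minor correction, worth making before the analysis because it is cheap.

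**What to change.** 1. Extend codes 1080 and 1090 to Prevenar 13.
2. Add a separate ATP-only condition for a Prevenar 13 booster that was not administered. Leave 1030 unchanged so that the TVC is unaffected.
3. Apply these Prevenar 13 conditions at antigen level: remove the infant from the ATP pneumococcal rows and keep the infant in the Infanrix hexa rows.
4. For omitted doses, state in SAP section 8 that keeping the infant in the Infanrix hexa rows departs from the ATP definition in protocol 10.4.3, and align SAP 4.1.3 and 4.1.4. If the sponsor does not want that departure, apply the existing 4.1.3 exclusion explicitly, through a code, to all antigens.

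The cost is a few lines of SAP text, one flag, and slightly fewer infants in the pneumococcal rows. The flag also needs a link to the temperature-excursion forms: protocol 5.2.2.1.1 puts the treatment number in the eCRF, but protocol 6.2 reports excursions on a separate form, and the documents do not show that these reach the eCRF.
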